12	PUBLICATION PLAN.....	12
13	REFERENCES.....	13
14	ATTACHMENTS.....	15

List of Abbreviations

CCRC – Clinical Cancer Review Committee
DSMAC – Data Safety Monitoring and Accrual Committee
mL - Milliliter
MRSA – Methicillin-resistant Staphylococcus aureus
NCCC – Norris Cotton Cancer Center
NCCN – National Comprehensive Cancer Network
SSI – Surgical Site Infection
S-SSI - Superficial surgical site infection
D-SSI – Deep surgical site infection
O-SSI – Organ space surgical site infection
SCIP – Surgical Care Improvement Project
PDS – Polydioxanone
SSO – Surgical Site Occurance

Study Summary

Title	Stoma Closure and Reinforcement Trial (SCAR) – Pilot Study
Short Title	SCAR Trial
Protocol Number	1
Phase	Pilot feasibility
Methodology	Open Label
Study Duration	The study is estimated to last 5 years
Study Center(s)	Single center – Dartmouth Hitchcock Medical Center
Objectives	
 1. To perform a pilot study to validate the mesh implantation procedure at the time of ileostomy closure. 2. To evaluate patient satisfaction and resource utilization associated with the procedure. 3. To prospectively evaluate the cohort for evidence of hernia formation at the previous stoma site. 4. Use data from this trial to design an appropriately powered, multi-center, prospective randomized, controlled trial of mesh reinforcement of ileostomy closures.
Number of Subjects	20
Diagnosis and Main Inclusion Criteria	
 1. Left sided colon or rectal cancer treated with resection and diverting loop ileostomy, with or without neoadjuvant or adjuvant therapy. 2. Age > 18years 3. Patient is undergoing elective closure of diverting loop ileostomy
Study Product, Dose, Route, Regimen	Bard™ Soft Mesh (Bard Davol, Inc): large pore, open weave, monofilament polypropylene mesh.
Duration of administration	The mesh would be implanted as a reinforcement of the stoma closure on a permanent basis. The mesh is not intended to be removed.
Reference therapy	Standard procedure for ileostomy closure
Statistical Methodology	No power calculation is necessary for this study since it is a pilot study. The results will be used to calculate power for future investigations.

1 Introduction

This document is a protocol for a human research study. This study is to be conducted according to US and international standards of Good Clinical Practice (FDA Title 21 part 312 and International Conference on Harmonization guidelines), applicable government regulations and Institutional research policies and procedures.

1.1 Background

Survival from colorectal cancer is continually increasing due to advances in multi-modality therapies leading to a growing cohort of patients with a history of the disease. Many of these patients will have long term complications from these treatments leading to a reduced quality of life. Minimally invasive approaches and enhanced recovery protocols have improved patient tolerance of colorectal cancer resection and reduced short term complications. Technologic improvements have allowed sphincter preserving surgery to be offered to a greater proportion of patients and therefore avoid permanent ostomies. However, temporary ostomies are often used as part of sphincter preserving surgery to minimize the consequences of a complication at a downstream anastomosis, and subsequently closed when clinically appropriate. Eventual restoration of intestinal continuity and closure of the ostomy puts patients at risk of developing a hernia at that site – a complication that occurs in approximately one third of patients¹⁻⁵. What is not known is whether the strategies used to treat other types of abdominal wall hernias will be applicable in this situation due to its unique circumstances. There is a critical need to develop an intervention to reduce the incidence of hernia formation at the site of previous ostomies as these hernias at minimum reduce quality of life through chronic pain and disfigurement and at worst may require emergency surgery for intestinal obstruction. Without an improvement in technique, it is likely additional patients will experience this complication as the colorectal cancer survivor cohort grows.

Incisional hernias are common occurrence with an incidence ranging from 10 to 58%.^{1,6} Risk factors include obesity, malnutrition, immunosuppression, connective tissue disorders, and previous abdominal surgery.⁷⁻¹¹ While some of these risk factors (like smoking) may be modifiable, others (such as the level of wound contamination) are not.¹² Although often amenable to minimally invasive approaches, colon and rectal procedures will frequently require a laparotomy type incision to extract bulky tumors.¹³ Open procedures are unlikely to be entirely replaced by minimally invasive approaches in colorectal practice and these hernias will remain a significant clinical burden both for the patient and the clinician.

One such incisional hernia is particularly challenging: the hernia at the site of a prior intestinal ostomy.^{1,3,4,6,14,15} The most common ostomy used for temporary intestinal diversion for colon and rectal cancer is the diverting loop ileostomy (herein referred to as ileostomy), which is an ostomy fashioned from the terminal segment of the small intestine. An ileostomy is used to protect a downstream anastomosis while patients heal or undergo adjuvant chemotherapy, and is preferred over colostomies due to the comparative ease of construction, ease of reversal, and a low rate of complications. They may be closed at a later time, as dictated by the patient's underlying disease process, restoring intestinal continuity. Hernias at the site of previous stoma placement are poorly understood, but are estimated to occur in up to a third of patients.¹⁻⁵

Reinforcement of an ileostomy closure with mesh is a novel approach to addressing a clinical scenario that bears many similarities to an abdominal wall hernia. Ileum protrudes through a fascial defect but for the purposes of diversion of the fecal stream rather than as the result of a congenital condition or iatrogenic process in a previous surgical site. Primary repair of fascial defects, as is commonly performed for closure of ileostomy, is not well supported in the literature for repair of abdominal wall hernias because of an unacceptably high recurrence rate, reported at up to 43%.¹⁶ Nearly all ostomies will have a fascial defect greater than 2cm which is where most surgeons would consider using mesh for a primary hernia repair such as an umbilical hernia.¹⁷ Incorporating mesh, whether biologic or synthetic, decreases the failure rate of repair.¹⁶ While underreported in the literature, most ostomies will have parastomal herniation of preperitoneal fat if not intraabdominal structures, indicating the ostomy defect has increased in size and adding further evidence to support addressing stoma takedown as a true hernia repair.⁶ Historically, the data for repairing hernias argues against utilizing mesh in a contaminated or clean contaminated field due to concerns of significant complications such as infections, mesh erosion, bowel adhesions, fistula formation, and pain.¹⁸⁻²⁰ Biologic meshes have been used in these situations, with the prevailing theory being that biologics are more resistant to infection.^{21,22} More recent data suggesting that sublay placement of a macroporous mesh of lightweight permanent or bioabsorbable

synthetic materials are relatively resistant to chronic infection challenge this notion, perhaps indicating the design and plane of implantation rather than material of the mesh are most important.²²⁻²⁵ Other reports have suggested the safety of ventral hernia repairs with mesh placement concurrently with colorectal surgery.²⁶ Recent trial data have also suggested greater effectiveness in reduction of hernia recurrence at two years from time of repair compared to biologic mesh in similar wound classifications in addition to fewer wound occurrences in the post-operative period.²⁷ The cost advantages of macroporous and bioabsorbable mesh have also been reported as superior to biologic mesh.^{28,29}

Anatomical positioning of the mesh during the hernia repair may also impact both the short term complications and the long term durability of the procedure. Three broad categories classify mesh placement: onlay, underlay, and sublay. Onlay is positioning of a mesh over a closed fascial incision in the subcutaneous space. Underlay is positioned within the peritoneal cavity beneath the closed fascial incision. The sublay (retro-rectus) position is within the muscular layers of the abdominal wall where fascial planes are closed on both sides of the mesh (Figure 1). Multiple reports have indicated intraperitoneal placement of mesh is associated with a higher recurrence rate compared to sublay or onlay techniques, with the sublay associated with the most favorable long term outcomes.³⁰⁻³²

Previous efforts to reduce formation of hernias have been described as having fair success, however they are limited by heterogeneity both in patient selection and in technique.³³⁻³⁷ These studies have used suboptimal anatomic positioning of the mesh reinforcement and are further limited by lack of consideration of consistency of technique between surgeons and consideration of associated resource costs.

Quality of life after sphincter sparing surgery in colorectal cancer is highly variable and correlates to the proximity of the anastomosis to the anal canal, which is inversely proportional to amount of rectum removed.³⁸ Technologic advances has allowed more patients to undergo sphincter-preserving surgery than has previously been possible.³⁹ Given that most patients undergoing sphincter-preserving surgery for distal colorectal cancer will also undergo temporary proximal diversion, minimizing the quality of life reduction of this portion of the procedure is imperative. It is well known hernias are associated with a reduced quality of life.⁴⁰

[figure not shown]

Figure 1. Sublay (Retro-rectus) placement of mesh (highlighted in green)

Our long-term goal is to develop a technique for closure of ostomy sites that minimizes the potential for hernia formation. The current literature is limited by a lack of prospective evaluation of the effectiveness of reinforcement of ostomy closure sites. Therefore, prospectively evaluating the technique will yield a more detailed understanding of how and when hernia formation at the ostomy closure site occurs and the presence of any unexpected findings. Our overall objectives in this study protocol, which is the first step towards our long-term-goal, are to (i) validate our ostomy site closure technique incorporating prosthetic mesh and calculate its associated costs, (ii) measure and compare patient reported quality of life pre- and post-intervention, and (iii) prospectively evaluate the incidence of hernia at

the stoma closure site at 6-months post procedure. Our central hypothesis is that a mesh reinforcement of the site during closure of an ostomy is safe and will reduce the incidence of hernia over time. The rationale for this project is that survival from colorectal cancer will continue to increase and improving the quality of life of patients by reducing long term complications of surgical therapy can be achieved through improvements in technique.

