By the completion of this pilot study, our expected outcomes are to have demonstrated a high level of procedural fidelity among the operating surgeons of the modified ostomy closure technique and comparable costs to the standard procedure as well as greater than 80% recruitment and retention of eligible participants, and greater than 90% adherence to the study protocol. We also expect to preliminarily demonstrate safety and similar quality of life compared to historical controls on short term follow-up. These results are expected to inform development of an appropriately powered, multiple center, randomized controlled trial comparing the effectiveness of our novel modification of ostomy closure technique to the standard technique.

3 Study Design

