3.3 Secondary Study Endpoints

The secondary endpoints will be evaluation of the incidence of hernia formation at the ileostomy site on a prospective basis at 30 days and 6 month intervals thereafter until two years from the date of ileostomy closure. The Promis SF 2.0 8a Ability to Participate in Social Roles and Activities instrument will be used to assess quality of life and the Colorectal Functional Outcome (COREFO) instrument will be used to evaluate bowel function at each interval.

4 Subject Selection and Withdrawal

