4.4.2 Data Collection and Follow-up for Withdrawn Subjects

Data related to the time period of the subject's participation will be included in the analysis of the treatment effect. Should a subject be withdrawn from the study for any reason, survival data will be maintained in accordance with the guidelines for follow-up prescribed by the NCCN.

5 Study Procedures

5.1 Encounter 1

Patients will be assessed for ileostomy closure based upon completion of therapy after primary resection of their malignancy. Appropriate candidates will be determined at the operating surgeon's discretion based on customary evaluation of clinical status. The informed consent process will be initiated and the patient recruited into the study.

5.2 Encounter 2

This encounter is the operative procedure. The procedure for closing the ileostomy (i.e. bowel anastomosis) will be at the discretion of the surgeon, provided it is performed through the ileostomy site without additional laparotomy incisions. In accordance with SCIP guidelines, pre-operative intravenous antibiotic and subcutaneous pharmacologic venous thromboembolism prophylaxis will be administered. Patients with a history of MRSA infection will also receive a dose of intravenous vancomycin prior to the procedure.

The abdominal wall reconstruction portion of the procedure will be standardized to ensure consistency between surgeons. The posterior rectus sheath is closed with native tissue either primarily, using hernia sac if present, or bridged with Vicryl-type mesh and a quickly absorbing suture material. This is done to isolate the mesh from the peritoneal cavity. The retrorectus plane is developed using electrocautery and blunt dissection to provide adequate placement of mesh such that it overlaps the posterior sheath defect by a minimum of 3cm on all sides. The mesh is placed in this plane and secured in place with slowly absorbable monofilament (0-PDS preferred) sutures placed through the anterior fascia or with application of fibrin sealant at the surgeon's discretion. This space is then irrigated with

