250mL of bacitracin/neomycin/polymixin antibiotic solution, patients with a history of MRSA will have vancomycin added to this solution. The anterior rectus sheath is then closed in a running fashion with slowly absorbing monofilament suture (0-PDS preferred). Again, 250mL of antibiotic solution are used as irrigation. A closed suction drain may be left in the retrorectus space at the discretion of the surgeon. Scarpa's layer is closed if possible and then skin closed with a circumferential purse string absorbable suture and the subcutaneous cavity packed with Iodoform gauze. This gauze is then removed on post-operative day 2. Post operatively the patient will receive standard care.

5.3 Encounter 3, 4, 5, et al.

The patients will be seen at 30days following discharge from hospitalization for stoma closure for a clinical examination and then will undergo standard follow-up for their cancer surveillance in accordance with NCCN guidelines which include computed tomography imaging every 6 months. Concurrently, clinical cancer surveillance evaluation by the operating surgeon (in conjunction with surveillance visits by medical oncology) will be performed on the same schedule with evaluation of clinical evidence of hernia formation as well as assessment of patient experience with the stoma site as part of regular cancer surveillance visit. These images will be subsequently evaluated for radiographic evidence of hernia formation by a radiologist blinded to the presence of the mesh, which is radiolucent. Patients will be undergoing computed tomography evaluation primarily as part of their cancer surveillance, and this imaging is not obtained expressly for the purposes of this study, and are only secondarily utilized to screen for hernia occurrence. Patients will also undergo ultrasound examination of the ostomy closure site at 30d post operatively then on the same 6 month schedule. These images are obtained for the purposes of the study and are intended to be compared to the computed tomography findings to evaluate congruence of the two modalities. These visits occur on a prescribed schedule for a period of 5 years after cancer treatment has concluded, after which no further follow-up is required.

Sonographic evaluation of the stoma site will be obtained on the Supersonic Unit in the Advanced Imaging Center using an 8-15 mHz linear transducer.

Cine clips will include all margins of the mesh repair to ensure adequate coverage of the repair site.

SUPINE:

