All subjects for this study will be provided a consent form describing this study and providing sufficient information for subjects to make an informed decision about their participation in this study. See Attachment A for a copy of the Subject Informed Consent Form. This consent form will be submitted with the protocol for review and approval by the EC/IRB for the study. The formal consent of a subject, using the EC/IRB-approved consent form, must be obtained before that subject undergoes any study procedure. The consent form must be signed by the subject or legally acceptable surrogate, and the investigator-designated research professional obtaining the consent.

11 Study Finances

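### A pre- versus post-intervention quality-of-life comparison is an overall objective, but the protocol schedules no PROMIS 8a before ileostomy closure

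*Combined protocol and SAP*

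**What the plan says.** Section 1.1 (Background) closes with three numbered overall objectives for this protocol. The second is to "measure and compare patient reported quality of life pre- and post-intervention".

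Section 3.3 names PROMIS 8a as the quality-of-life instrument and COREFO as the bowel-function instrument. It is the only section that gives either a time. Its opening sentence sets the hernia assessments "at 30 days and 6 month intervals thereafter until two years from the date of ileostomy closure". The next sentence introduces PROMIS for quality of life and then says that the COREFO "instrument will be used to evaluate bowel function at each interval".

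The visit descriptions run as follows:

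- Section 5.1 (Encounter 1) covers candidacy for closure, and then "The informed consent process will be initiated and the patient recruited into the study". No questionnaire is listed.
- Section 5.2 (Encounter 2) begins "This encounter is the operative procedure" and lists no questionnaire.
- Section 5.3 (Encounter 3 onward) provides for "assessment of patient experience with the stoma site as part of regular cancer surveillance visit". These visits all follow closure.

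Section 6.3 (Statistical Methods) describes no change-from-baseline analysis. Section 6.4 takes everyone who had the study procedure as the analysis population, then leaves out of the final analysis anyone whose follow-up data are incomplete.

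**The concern.** A pre/post comparison within patients needs two scores per patient, one on each side of the operation. The plan provides for the second and not the first. The omission has a deadline: once the ileostomy is closed, the patient's state with the stoma can no longer be measured.

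At stake is one stated objective. Without a baseline the pilot can describe quality of life after closure but not how far it moved. It also cannot supply the variability of change, or the correlation between baseline and follow-up, to the randomized trial that it is meant to inform. Nor would it test whether pre-operative collection is practicable.

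**Working it through.** The documents state no figure to reproduce here. The check compares the objective with the schedule.

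**Inputs**

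- Planned patients: 20 (Study Summary; Statistical Plan).
- Quality-of-life instrument: PROMIS 8a (section 3.3).
- Times: 30 days, then six-monthly, ending two years after closure (section 3.3).
- Content of Encounters 1 and 2 (sections 5.1 and 5.2).

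**Step 1: what the objective needs.** Change for patient *i* = score after closure minus score before closure. Both terms must be observed.

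**Step 2: scheduled times, taking those in section 3.3 to apply to PROMIS.** With 30 days taken as month 1:

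| Reading of section 3.3 | Times (months after closure) | Before closure | After closure |
|---|---|---|---|
| Six-month steps counted from closure | 1, 6, 12, 18, 24 | 0 | 5 |
| Six-month steps counted from day 30 | 1, 7, 13, 19 (the next, 25, passes two years) | 0 | 4 |

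**Step 3: does another section add a pre-operative form?** Encounter 1 is candidacy, consent and recruitment. Encounter 2 is the operation. The patient-experience assessment in section 5.3 falls at surveillance visits after closure. Nowhere is either questionnaire tied to a baseline or pre-operative time.

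**Step 4: result.** Scheduled pre/post pairs = 20 patients × 0 pre-operative scores = 0 under either reading.

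**Step 5: is there an analysis waiting for such data?** Section 6.3 has none. If a paired analysis were added, section 6.4 as worded could still drop a patient who had both the baseline and the chosen follow-up score but missed a later visit. The two sections need to be changed together.

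**The case against.** The strongest reply is that the pre/post wording appears only in the Background. The objectives in the Study Summary and section 2, and the endpoints in section 3.3, contain no pre/post contrast. Secondary Objective #1 compares procedure-related aspects with bowel-function aspects instead. Aligning section 1.1 with section 2 would therefore be a legitimate repair. This stands as far as it goes, and that route is kept under the fix. It does not remove the conflict, because section 1.1 presents the comparison as an overall objective of this protocol.

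A second reply is grammatical. The timing phrase in section 3.3 ends the COREFO clause and may govern only that clause, which would leave PROMIS with no stated time at all. That is a fair reading, but it still schedules no baseline.

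A third is that the loss is limited. Every treated patient has closure and mesh at the same operation, with no concurrent control, so a change score could not show what mesh does to quality of life. This stands, and it limits how the change may be described.

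Stronger inferences are tempting, and the documents do not support them:

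- *That no baseline score will exist.* The documents show only that none is scheduled. Staff might collect one unprompted, though it would be neither standardized nor tied to an analysis.
- *That the missing COREFO baseline is part of the same defect.* The objective concerns quality of life, which section 3.3 assigns to PROMIS. COREFO can stay post-operative.
- *That the planned paper on patient-reported outcomes (section 12) depends on a baseline.* That section promises no pre/post analysis, and post-operative scores over time could fill such a paper.
- *That other quality-of-life wording adds weight.* Section 2 expects "similar quality of life compared to historical controls on short term follow-up", and Secondary Objective #1 leaves its contrast undefined. These are separate questions that a baseline form would not settle.

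**Conclusion.** The point holds in a limited form. Section 1.1 sets a pre/post quality-of-life objective, and the plan schedules no pre-operative PROMIS 8a: 0 planned baseline scores, hence 0 of 20 scheduled change scores. This rests on the text of sections 1.1, 3.3, 5.1 to 5.3 and 6.3 and on the planned 20 patients. It needs no assumption about standard deviation, correlation or attendance, and it is the same under either reading of the six-month intervals.

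It should be fixed before further patients are operated on, because the gap cannot be closed afterwards. It does not touch the 30-day wound endpoint or the measures of recruitment, retention and adherence.

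**What to change.** 1. **Sections 3.3 and 5.1:** add one PROMIS 8a before the operation. Section 5.1 only starts the consent process, and the Ethical Considerations section says that formal consent "must be obtained before that subject undergoes any study procedure". The form therefore belongs after signature, at Encounter 1 or a later pre-operative contact.
2. **Section 6.3:** state that paired change from baseline is reported with a 95% confidence interval at one pre-specified post-operative time, in treated patients with both scores. Six months is one option, since section 1.1 already uses it for hernia.
3. **Section 6.4:** word the exclusion so that incomplete later follow-up does not remove a patient who has both of these scores.
4. **Interpretation:** describe the change as recovery after closure with mesh, not as a mesh effect.

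If no baseline will be collected, remove the pre/post comparison from section 1.1 so that it agrees with the section 2 objectives.

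**Cost:** one short form per patient, 20 × 1 = 20 forms, and a protocol amendment submitted to the IRB. There is no added imaging or procedure, and the primary endpoint does not change.
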